will use our secure VA Research Server under the direction of [name] as the Study Data Core. All study related committees will meet at the offices of the VA Outcomes Group, either in person or using existing secure teleconference facilities. Web-based study team meetings will be held every other week, and will use videoconference to minimize expense. Two study meetings will be held at the annual meetings of the Association of VA Surgeons and at the Society for Vascular Surgery during each year of the study. This will serve as a cost-effective way for our group to meet biannually during the study period.

Characteristics and selection of the study population: Our study population will be Veterans and vascular surgeons enrolled at the ten intervention sites and ten control sites in our cluster-randomized trial. The inclusion criteria for patients will be Veterans with a >5.0 cm AAA that are candidates for endovascular and open repair. Step C of the Study Procedures describe the recruitment procedures and inclusion criteria in detail.

STUDY PROCEDURES

Step A: Recruitment of Surgeons Twenty VA hospitals that currently perform both endovascular and open repair are the study sample. Each local site investigator has been interviewed and their credentials vetted by the PI, and has accepted to participate in the study. Local site investigators may invite one or two additional surgeons whom they work with at their site to participate in the study. Site Study Coordinators will provide surgeons the Study Invitation and Information Sheet at the start of the study period and document the date. A waiver of documentation of informed consent for surgeons will be requested since the surgeon's participation involves no procedures other than completion of a survey and presents no more than minimal risk.

Step B: Selection of Intervention Centers: In Aim 1, we will conduct the intervention in 120 patients across 10 VA hospitals randomly assigned to the intervention arm. We will have a 9:1 stratified randomization scheme, so that we have a similar proportion of Complex and Intermediate Surgical VA hospitals in the intervention and control arms. These are the only two types of VA hospitals that perform AAA repair. Sites will be randomized at IRB approval in a rolling fashion. Site specific Study Coordinators will use the Study Protocol to facilitate IRB approval.^{3, 15}.

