The patient will be remunerated at completion of the enrollment visit. Data will be recorded securely by the Site Study Coordinator.

The Veteran will be thanked for their participation by the study team via a formal letter mailed from the Principal Investigator.

Process at the Control Sites:

Step 1: The Study Coordinator will administer the Survey. (10 minutes)

Step 2: The Study Coordinator will escort the patient to the visit with the vascular surgeon.

Step 3: After the Visit, the Site-Specific Research Coordinator will complete the Decision-Process Score with the Veteran. (5 minutes)

Step 4: Thirty days after AAA repair, the Study Coordinator will complete the PSQ-18 with the

Veteran. (5 minutes)

The patient will be remunerated at completion of the enrollment visit. Data will be recorded securely by the Site Study Coordinator.

The Veteran will be thanked for their participation by the study team via a formal letter mailed from the Principal Investigator.

Surgeon survey administration at both the intervention and control sites:

Step 1: The Study Coordinator will administer the Pre-Visit Survey to the surgeon (1 minute, according to pilot testing at four sites in the trial, and two sites outside the trial).

Step 2: The surgeon will have the clinic visit with the Veteran.

[figure not shown]
Step 3: After the Visit, the Study Coordinator will complete the Post-Visit Survey with the surgeon (1 minute).

Data will be recorded securely by the Study Coordinator.

Recruitment Target: We will recruit 12 Veterans per site (4 Veterans per site per month for 3 months) at 10 sites in the intervention arm for a total of 120 Veterans in the intervention arm. We will recruit 12 Veterans per site (4 Veterans per site per month for 3 months) at 10 sites in the control arm for a total of 120 Veterans in the control arm. The unit of analysis will be the Veteran. Randomization will occur at the site level, in a stratified 9:1 randomization scheme, based on the VA hospital's Surgical Complexity designation. We will enroll 8 Complex and 2 Intermediate sites per arm. Randomization will occur at the time of IRB approval. Weekly conference calls with Site Study Coordinators will assess study enrollment rates and help with problem-solving.

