Aim 1. Dependent and Independent Variables: The main dependent variable in Aim 1 is the preference for repair type (endovascular or open) as expressed by Veterans and surgeons in their respective survey instruments. Each survey instrument has a validated coding algorithm which will be used to categorize survey responses into preference for endovascular or open repair (Appendix 2)⁴⁴. Independent variables, such as age, gender, race, ethnicity, and other descriptive variables are recorded as part of the survey instrument by the Site Study Coordinator. Hospital and surgeon characteristics such as annual hospital and surgeon volume of endovascular and open repair for each participating site will be collected via VINCI by [name]. These variables will be measured at the hospital level, as in prior analyses.^{65, 97-100}

Aim 1: Data analytic strategy: tests, strengths, limitations, and alternative approaches: In Aim 1, our main outcome variable will be Veteran and surgeon preference for repair type (endovascular or open repair). The preference will be defined as either preference for endovascular or preference for open repair. Repair type preference will be categorized from several questions in our survey instruments. Several questions allow for differing degrees of choice (e.g., strongly/slightly favor open repair). For these responses, we will use variables that allow this category. We will use a coding algorithm (Appendix 2) which deconstructs survey questions into components that generate binary outcomes (i.e., preference for open or endovascular repair) and allows sensitivity analyses using the gradients. We will compare the proportion choosing each repair type in the intervention and control groups to test the effect of the decision aid on repair type preference. The proportions preferring each repair type will be compared between the two groups accounting for clustering of patients within center and/or surgeon; in particular, we will use the Mantel-Haenszel test (for stratified contingency tables, equivalent to partial likelihood ratio test from fixed effects logistic regression) or a mixed effects logistic regression with fixed effect of group, and random intercept for center effects.

Aim 1 Data Collection Strategy: potential problems and solutions Refer to Section 6 of this Protocol Coding Guide and Data Management Plan.

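### Aim 1 arm comparison: the Mantel-Haenszel option cannot account for site clustering, so one cluster-adjusted analysis should be named; the 9:1 site ratio also needs reconciling with the stated site counts

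*Combined protocol and SAP*

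**What the plan says.** **Analysis.** Section 7, Aim 1 data analytic strategy, sets a requirement for comparing repair preference between arms: it is to be done "accounting for clustering of patients within center and/or surgeon". It then offers two methods joined by an 'or'. The first reads "we will use the Mantel-Haenszel test (for stratified contingency tables", and the text describes this test as "equivalent to partial likelihood ratio test from fixed effects logistic regression". The second is a mixed logistic model with a fixed group effect and a random centre intercept. The strata of the first are not named, neither method includes the factor by which sites are randomised, and no choice is made between them.

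**Randomisation.** Section 4, Recruitment Target, says "Randomization will occur at the site level, in a stratified 9:1 randomization scheme", based on Surgical Complexity, and the next sentence says "We will enroll 8 Complex and 2 Intermediate sites per arm". Step B repeats the ratio ("We will have a 9:1 stratified randomization scheme") and gives its purpose: "so that we have a similar proportion of Complex and Intermediate Surgical VA hospitals in the intervention and control arms". The paragraph on the study population refers to "ten intervention sites and ten control sites in our cluster-randomized trial". Nothing defines what the 9 and the 1 count.

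**The concern.** In a cluster-randomised trial every patient at a site is in the same arm. A test that conditions on site therefore has nothing to compare, and a test that ignores site treats correlated patients as independent. A stratified Mantel-Haenszel test does one or the other, depending on the strata, so it cannot deliver the clustering adjustment that the same sentence promises. Leaving it as an alternative also leaves the main Aim 1 comparison unspecified.

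The randomisation ratio is a smaller matter. It disagrees with the site counts beside it, so the allocation rule cannot be stated accurately from the text alone.

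**Working it through.** **Inputs.** Ten sites per arm and 12 Veterans per site (Section 4, Recruitment Target); control preference for endovascular repair 0.90, 0.68 under the 25% relative decline, and ICC 0.01 to 0.10 (Section 7, Aim 1 power analysis and Table 3). Assumed: two-sided 5% level (Aim 1 states none) and equal site sizes.

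**1. The plan's own power figure.** Effective patients per arm = 120 / (1 + 11 × ICC).
- ICC 0.01: 120 / 1.11 = 108.1. SE = √[(0.90×0.10 + 0.68×0.32) / 108.1] = √(0.3076 / 108.1) = 0.0533. Noncentrality is 0.22 / 0.0533 ≈ 4.12. Power by noncentral t on 18 df is 97.4%; the plan says 96%.
- ICC 0.10: 120 / 2.1 = 57.1, SE 0.0734, noncentrality 3.00, power 80.9%; the plan says 81%.

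The stated power is therefore close to that of a 10:10 trial whose analysis carries the design effect.

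**2. Mantel-Haenszel stratified by centre.** At an intervention site n₁ = 12 and n₀ = 0. If m Veterans prefer endovascular repair, the observed count is m and the expected count is 12m/12 = m, a difference of 0. The stratum variance n₁n₀m(N−m) / [N²(N−1)] is 0 because n₀ = 0. Control sites behave the same way, so the statistic is 0/0 over all 20 strata. In the fixed-effects logistic equivalent, arm is the sum of the ten intervention-site indicators: 20 centre indicators plus arm have rank 20, not 21, and arm is not estimable. Stratifying by surgeon fails likewise, because Section 4, Step A recruits surgeons within a site.

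**3. Mantel-Haenszel stratified by complexity only.** This can be computed, but its variance is too small by the factor 1 + 11 × ICC. The true rejection rate under the null is about 2[1 − Φ(1.96 / √(1 + 11 × ICC))]. The first simulation used beta-binomial data, 20 sites of 12, 8 + 2 per arm, preference 0.90 in both arms and 20,000 trials. The continuity-corrected figures come from a second simulation of 40,000 trials, whose uncorrected results agree with the closed form.

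| ICC | 1 + 11 × ICC | Closed form | Simulated | With continuity correction |
|---|---|---|---|---|
| 0.01 | 1.11 | 6.3% | 5.9% | about 4% |
| 0.05 | 1.55 | 11.5% | 11.0% | about 8% |
| 0.10 | 2.10 | 17.6% | 17.3% | about 13% |

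**4. The mixed model with 20 clusters.** With the stratum term and an uncorrected likelihood-ratio test, null rejection was 4.2%, 7.2% and 7.5% at ICC 0.01, 0.05 and 0.10 (600 trials each, Monte Carlo error about 1 point). A separate check at 0.05 and 0.10 (400 trials each, error about 1.4 points) gave 8.5% and 8.3% uncorrected, against 5.5% and 6.3% with F(1,17). A site-level t test with the stratum on 17 df gave 4.0%, 4.7% and 4.0% (600 trials each).

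**5. Cost and benefit of the stratum term.** Moving from 18 to 17 df changes power for 0.90 vs 0.68 from 97.4 / 91.0 / 80.9% to 97.3 / 90.8 / 80.7% at the three ICCs. The benefit depends on a Complex-Intermediate gap in preference that the documents do not give. With assumed gaps of 5 to 20 points and an assumed residual ICC of 0.03, a site-level test of 90% vs 67.5% gains 0.3 points (94.8 to 95.1%) to 5.6 points (90.4 to 96.0%).

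**6. The ratio.** Read as a site mix, 9:1 of ten sites is 9 + 1 per arm (18 + 2 overall); the text says 8 + 2 (16 + 4 overall), which is 4:1. Read as an arm allocation, 9:1 of 20 sites is 18:2, or 216 vs 24 Veterans; the text says 10:10 and 120 vs 120. Neither reading fits.

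**The case against.** **The plan may never use an invalid test.** The text does not mention complexity strata, and its wording points to centre. On that reading the test returns nothing and the analyst falls back on the mixed model already offered. This stands: a reader might infer that the plan commits to a test with an 18% false-positive rate, and the documents do not support that. The figure needs both an unstated choice of strata and the top of the plan's ICC range; at its planning ICC of 0.01 the rate is about 6%, or 4% with continuity correction. What remains is that no reading of the option meets the clustering requirement.

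**Leaving out the stratum is not an error.** This also stands. A reader might infer bias or inflated error, but omitting a balanced stratum from the mixed model makes the test conservative if anything: in the site-level simulation, null rejection without the term was 4.4% at a 5-point gap and 1.2% at a 20-point gap. Large gains need large gaps. A 20-point gap alone implies between-site variance 0.8 × 0.2 × 0.20² = 0.0064, and 0.0064 / 0.09 is an ICC of 0.071. Adding the term is good practice at negligible cost.

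**The 9:1 ratio is only wording.** Agreed. A reader might infer an 18:2 trial, or a wrong sample size. The site counts, the 120 per arm and Table 3 all use 10:10. By a pooled z formula at ICC 0.01, an 18:2 split would give 76.6% power (18 control sites) or 59.1% (18 intervention sites), far from the stated 96%. A reader might also take 8 + 2 as correct and 9:1 as the slip. The documents do not show that, and the site list is incomplete in the text reviewed, so stratum totals cannot be counted.

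**Conclusion.** The Mantel-Haenszel option is wrong as written for the Aim 1 arm comparison. By centre or surgeon it is not estimable, which follows from site-level randomisation and needs no assumption. By complexity alone it rejects a true null about 6%, 11% and 18% of the time over the plan's own ICC range, given equal sites of 12 and a two-sided 5% level. The mixed model is the sound choice of the two, but with 20 clusters it needs a small-sample reference distribution, and Section 7 names none. The case for the stratum term rests on its very small cost and on matching the randomisation; any power gain depends on an assumed gap.

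The 9:1 ratio contradicts the stated counts under both readings. It is a secondary point with no effect on sample size or power.

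**What to change.** **Section 7, Aim 1.** Delete the Mantel-Haenszel option for the arm comparison. Name one analysis: logistic regression with a random centre intercept, fixed effects for arm and Surgical Complexity, and a small-sample reference distribution for 20 clusters, for example F with 1 and 17 df. A t test on site proportions with the stratum, on 17 df, is an acceptable alternative if named in advance as the single analysis.

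**Section 4, Step B and Recruitment Target.** Replace the undefined ratio with two explicit statements: the allocation ratio between arms within each complexity stratum, and the number of Complex and Intermediate sites in each arm. If sites are already randomised, report the scheme and counts actually used.

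**Cost.** One between-site degree of freedom (0.1 to 0.2 points of power for 0.90 vs 0.68), removal of one optional test, and wording edits in two places. Sites, sample size and Aim 2 do not change.

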Before the advent of endovascular devices in the late 1990s, open surgical repair of AAA was the only treatment option for patients with AAA. In open surgical repair, a large abdominal incision is necessary, and clamps are applied to the aorta - the largest blood vessel in the body. Surgical reconstruction is performed as shown in Figure 1. The risk of perioperative death is 3-5% for open AAA repair, even in hospitals skilled in this major operation. The chance of major complications such as bleeding, need for further surgery, or heart attack, can approach 20% within the first year.¹⁰⁻¹³

The development of endovascular AAA repair (called EVAR) in the 1990s changed the treatment options available for patients with AAA¹⁴. Stent-grafts could be placed through small incisions in the groins to exclude the aneurysm from blood flow, without any need for a large abdominal incision or aortic clamping (Figure 2). Short term recovery was now much simpler, and vascular surgeons rapidly adopted this new technique.

Equipoise between repair types for AAA:

Endovascular repair and open surgery have been compared extensively in a variety of settings, including large randomized trials within VA^{1-3, 9}. In these studies, the less-invasive nature of endovascular repair demonstrated several advantages: lower rates of perioperative mortality (less than 2% versus 5%), shorter length of stay (2 versus 7 days), and better patient quality of life earlier after AAA treatment¹⁵. However, endovascular repair had clear disadvantages as well. For example, Veterans treated with EVAR commonly develop leaks around their graft called endoleaks, which can require secondary procedures, and can result in late aneurysm rupture¹⁶⁻²¹.

These tradeoffs have made it difficult to find a clear “winner” between endovascular repair and open surgery. While the randomized trials gave surgeons and Veterans important information about the short and long-term outcomes of each approach, they failed to identify a single AAA repair type that would be best for all Veterans with AAA. Because of these tradeoffs, equipoise still remains as to the optimal AAA repair type.

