The risk of a confidentiality breach is minimized by the fact that these data will be maintained on the White River Junction VAMC's dedicated research server, behind the VA firewall. Only summary statistical analyses are ever exported from the server. Data analysts for this project will use only the anonymous study IDs to distinguish individual subjects; they will not have access to any other personal identifiers, nor will they be able to convert Study IDs to SSNs. The risk of a data breach that will compromise personal information is minimal.

Potential Benefits of Research to Subjects and Others.

There are no direct benefits to Veterans or surgeons participating in this research. There is a potential benefit for Veterans enrolled in the intervention arm of this study, which is clearer pathway for communicating their preferences about their abdominal aortic aneurysm to the surgeon treating their aneurysm. Further, the information to be derived will be of great value for the planning of future interventions and resource allocation to provide Veterans the best access to the highest quality care for high-risk surgical interventions such as AAA repair.

Importance of Knowledge to be Gained.

This study will yield new information about outcomes for expensive and high-risk conditions/ procedures to support the planning of optimal resource allocation. It will distinguish VA facilities that achieve the best outcomes for further study, and it will identify the components of inpatient services that yield the best outcomes for Veterans with AAA. The knowledge to be gained will help VA planners improve access to care for patients with high-risk surgical conditions, and the benefits will greatly outweigh the limited risks to confidentiality and patient safety.

Data and Safety Monitoring Plan.

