As this study involves a survey only, we do not anticipate any serious adverse events related to the research, and that any adverse events which occur during the study period are likely to be related to underlying, pre-existing medical conditions, and/or the surgery. Therefore, we will not routinely collect any data to assess harms. The Data and Safety Monitoring Committee will be responsible for ensuring that data conduct is commensurate with any potential benefits or harms evident in quarterly analysis of study datasets. **Any unanticipated problems which may arise involving risks to subjects or others, related to research (including data integrity/security issues) will be documented and reported to the IRB within 5 business days after becoming aware of the event, in accordance with VHA Handbook 1058.01 Paragraph 6.** This study will adhere to the **VA Central IRB Table of Reportable Events.** Data accuracy and integrity will meet the standards for VA or Medicare administrative treatment files.

5. Study Committees

We have established a study committee structure as outlined below, consisting of three central committees: A Steering Committee, A Data Safety Monitoring Board, and a Publications Committee. The committees are staffed by Key Personnel and six experienced, VA-funded surgical investigators ([name], [name], [name], [name], [name], and [name]). Each Committee will meet quarterly during the study period.

AAA Survey Study Steering Committee,

[name],

[name],

[name],

[name],

[name],

[name],

[name],

[name],

[name]

[name]

AAA Survey Study Data Safety Monitoring Board

[name]

[name]

[name] (external auditor)

AAA Survey Study Publications Committee:

[name]

[name]

[name]

6. Coding Guide and Data Management Plan

Procedures for managing the flow of information from participating sites is detailed below. Any deviation from these procedures that might be relevant to participant protection will be reported to the PI within 24 hours. The PI will have 24 hours to investigate the occurrence and convey the information to the VA Central IRB. All study

team members must adhere to the **VA Central IRB Table of Reportable Events** all documented VA security policies and protocols. Removal of access to research study data will be accomplished for study personnel when they are no longer part of the research team.

Step 1:

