Each completed survey and consent form will be completed by the Veteran under the supervision of the site-specific Study Coordinator.

Step 2:

A PDF of the survey document will be created and sent via secure email to a file maintained on our Research Server by the Data Coordinating Center (led by [name] and [name] at White River Junction).

Step 3:

After confirming secure receipt and upload of the PDF onto our Research Server, the Site Study Coordinator will store the original documents in a locked file until study conclusion. Original documents will be destroyed in accordance with the VA Records Control schedule.

Step 4:

The survey data will be extracted by our Central Study Coordinator and imported into analytic software files (SAS) to allow for analysis by Drs. [name] and [name]. A Coordinating Center Research Nurse will facilitate this effort as well, and hold biweekly technical support calls with the Central Site Study Coordinator with all sites during the study period. All research datasets will be destroyed in accordance with the VA Records Control Schedule.

Long term follow-up Data Collection:

To inform the agreement between preferences and repair type, we will compare the preference identified for each Veteran in Aim 1 and the actual AAA repair type the Veteran receives.

This will be done at each site by the Site Study Coordinator who will have access to PHI of participants enrolled only at their site for the purpose of follow-up. They will not have access to study data or PHI from any other study sites.

Every three months during the Study Period, each site-specific Study Coordinator will audit CPRS for each enrolled Veteran at that site.

If no record of repair exists, the Site Coordinator will contact the enrolled patients via phone to ensure repair has not been performed outside of VA.

Patients who do not undergo repair or who die prior to repair will be excluded from this step in the analysis.

7. Data Analysis

(Please note: The following sections are described separately for Aim 1 and Aim 2).

Aim 1: To identify Veteran and surgeon factors associated with preference for endovascular or

open repair.

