To identify patient characteristics (such as survey responses) associated with preference for endovascular or open repair we will use multivariable mixed effects logistic regression. The use of mixed effects is to account for clustering within individual VA centers using a random intercept, e.g. $\text{logit } \text{Pr}[Y_{ij}=1]=X_{ij}\beta+\mu_i$ where Y_{ij} is the binary preference variable in subject j from cluster i , X_{ij} is a vector of characteristics, μ_i is a random intercept from a zero mean distribution with standard deviation to be estimated (e.g. normal), and β is a vector of coefficient(s). We will explore the feasibility (e.g. convergence) and sensitivity of findings of patient characteristics of using either a random intercept for surgeon, or for center, or for surgeon nested within center. We will report both unadjusted and adjusted estimates, after identifying one or more models to adjust for using for instance stepwise regression or LASSO. Stata (e.g., xtmelogit) and/or R (library lme4 or nlme) software will be used. [name] has extensive experience in these strategies.

Missing Data: To accommodate missing data where justified (e.g. the variable with missing data is predictive and deserves to be adjusted for, and furthermore the data is believed to be missing at random) we shall use multiple imputation methods, such as implemented in the Stata *mi* routine.

Power Analysis: Comparing the effect of the decision aid on repair type preference. Because the decision aid will inform Veterans more fully about the long-term disadvantages of endovascular repair, we hypothesize that the decision aid will reduce the proportion of Veterans who prefer endovascular repair by 25%, based on similar decision aids studied in surgical settings in breast cancer and back pain¹⁶⁻¹⁸.

Table 3 Sample size and power calculations (assuming a 90% baseline rate of EVAR preference)

Number of clusters	Number of patients per cluster	Total Number of Patients	Proportion Choosing Endovascular Repair At	Decision Aid Effect Size (in relative decline in preference)	Proportion Choosing Endovasc Repair at	Power To detect significant difference	Power To detect significant difference	Power To detect significant difference
--------------------	--------------------------------	--------------------------	--	--	--	--	--	--

Intervention	Control	Intervention	Control	Intervention	Control	Control Sites for endovascular	Intervention Sites	(ICC 0.01)	(ICC 0.05)	(ICC 0.10)

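### Harms data are waived because the study is called a survey only, yet the decision aid is expected to shift repair choice and no post-repair clinical outcome is collected

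*Combined protocol and SAP*

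**What the plan says.** The Data and Safety Monitoring Plan in Section 4 opens with its premise: "As this study involves a survey only, we do not anticipate any serious adverse events related to the research". It attributes any events that do occur to pre-existing illness or to the operation, and concludes: "Therefore, we will not routinely collect any data to assess harms". The next sentence asks the monitoring committee to ensure that data conduct is "commensurate with any potential benefits or harms evident in quarterly analysis of study datasets". The other safety route is for unanticipated problems related to the research, which "will be documented and reported to the IRB within 5 business days after becoming aware of the event".

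Elsewhere the plan describes more than a survey. The intervention arm receives a decision aid as well as the survey (Section 4, Study Design and Step D). In the Aim 1 power analysis (Section 7), "we hypothesize that the decision aid will reduce the proportion of Veterans who prefer endovascular repair by 25" percent, which Table 3 shows as 0.90 in control against 0.68 in intervention. The Aim 2 power analysis expects treatment to follow preference more closely, with kappa rising from 0.7 to 0.88.

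The Introduction gives perioperative mortality as below 2% for endovascular repair and 5% for open repair (3-5% for open repair in the Background text), and length of stay as 2 against 7 days.

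On follow-up, Section 6 says: "Every three months during the Study Period, each site-specific Study Coordinator will audit CPRS for each enrolled Veteran at that site". The stated purpose is to learn which repair was done. Finally, under Importance of Knowledge to be Gained, the plan says of the study: "It will distinguish VA facilities that achieve the best outcomes for further study".

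**The concern.** The reason given for collecting no harms data does not fit the trial described. The aid is meant to change what Veterans prefer and, through better agreement, may change which operation they receive. Events caused by the operation cannot then be set aside as unrelated to the research, because the choice of operation lies on the path from randomisation to outcome.

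Followed as written, the trial could report that the aid shifted choices and improved agreement without being able to say how many Veterans in each arm died within 30 days of repair, ruptured or needed re-intervention. The monitoring committee is pointed to harms visible in the study datasets, but no variable for a clinical event after repair is planned. The route to the IRB is unlikely to fill the gap: it covers unanticipated, research-related problems, and a perioperative death is a known surgical risk that the plan has already attributed elsewhere.

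There is also a practical cost. The PSQ-18 is given 30 days after repair. Unless deaths are recorded, a missing questionnaire could be a death or a non-response.

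**Working it through.** **Inputs**
- 120 Veterans per arm (Section 4, Recruitment Target); 85% repaired (Definition of Usual Care). Repaired per arm: 120 × 0.85 = 102.
- Endovascular preference: control 0.90; intervention 0.68, 0.73 or 0.78 as printed in Table 3.
- Perioperative mortality: open 5%, or 3% at the lower figure; endovascular stated only as below 2% and taken here as 2%.
- Kappa 0.7 (control) and 0.88 (intervention), from the Aim 2 power analysis.

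**Step 1: the plan's own figures.** 0.90 × (1 − 0.25) = 0.675, printed as 0.68. The stated 96% power at ICC 0.01: design effect 1 + 11 × 0.01 = 1.11, so effective n = 120 / 1.11 = 108.1 per arm. With two-sided alpha 0.05 (assumed, as Aim 1 states none), a plain two-proportion calculation gives 0.98. A t reference on 18 degrees of freedom plus a continuity correction gives 0.96. The figure is reproducible, and nothing below depends on it.

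**Step 2: open repairs and deaths if preference is fully converted to treatment.** Extra open repairs = 102 × (0.90 − p). Extra perioperative deaths = extra open repairs × (open − endovascular mortality).

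| Table 3 effect | p | Extra open repairs | Extra deaths, 5% vs 2% | Extra deaths, 3% vs 2% |
|---|---|---|---|---|
| 25% | 0.68 | 22.4 | 0.67 | 0.22 |
| 20% | 0.73 | 17.3 | 0.52 | 0.17 |
| 15% | 0.78 | 12.2 | 0.37 | 0.12 |

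If the 10% dropout also applies, the top row falls to 120 × 0.90 × 0.85 × 0.22 = 20.2 extra open repairs. If endovascular mortality were zero, the extreme bound of below 2%, the top row would give 22.4 × 0.05 = 1.1 extra deaths.

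**Step 3: relaxing full conversion, using the plan's kappas at the 25% effect.** Kappa = (observed − chance agreement) / (1 − chance agreement), solved for the proportion receiving open repair.
- Preferred and received proportions equal in each arm: 22.4 extra.
- All disagreements towards endovascular repair: received open 0.056 and 0.270, so 102 × 0.214 = 21.8 extra.
- All disagreements towards open repair: 0.171 and 0.375, giving 20.8 extra.
- Disagreements in opposite directions in the two arms: about 10 to 32 extra.

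**Step 4: could the arms be compared formally?** Expected perioperative deaths at 5% and 2%:
- Control: 10.2 × 0.05 + 91.8 × 0.02 = 2.3.
- Intervention: 32.64 × 0.05 + 69.36 × 0.02 = 3.0.

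Power to detect this difference is about 5%, even before allowing for clustering.

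**Step 5: what the board would and would not have.**
- Available: repair type, deaths before repair (identified so that they can be excluded from the agreement analysis), the Decision Process Score, the 30-day PSQ-18, the 30-day Decision Regret Scale named under Study Design, and unanticipated-problem reports.
- Not planned anywhere: death after repair, complications, rupture, re-intervention or length of stay.

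**The case against.** A fair defence has five parts.

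**The plan predicts preference, not operations.** A reader might infer that the plan expects about 22 Veterans to be moved to open repair. It does not say so. Table 3 concerns stated preference, the choice of repair is left to the surgeon's judgement, and agreement is not assumed perfect. The figure of 22 needs full conversion and the largest of three tabulated effects. Taking 10% open repair in control also equates preference with treatment, although the Introduction reports 33% open repair in VA. This stands, so a range with its assumption is the most that can be claimed.

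**The board is not empty-handed.** A reader might infer that it has nothing to review. Step 5 of the working shows otherwise, and decision regret is arguably the harm closest to a decision aid. The wording also says not routinely rather than never, and the sentence about the committee concerns data conduct rather than a promised harms comparison. This stands in part: what is missing is any clinical outcome after repair.

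**Net harm is not shown.** A reader might infer that the aid steers Veterans to the worse operation. The Abstract describes similar survival within two years and greater durability with open repair, and the Introduction calls aneurysm-related and overall mortality equivalent. This stands. Nor can the Introduction's figure of up to 20% major complications be used to compare arms, because no matching figure is given for endovascular repair. But an exchange of early for late risk is a reason to record both, not neither.

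**The aid only standardises information usually given in clinic, to Veterans eligible for both repairs.** Potential Risks for Veterans says this, and it supports a minimal-risk classification. It does not remove the conflict with a hypothesised 25% fall in endovascular preference.

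**The data would be imperfect.** Study dates are removed from datasets, and repairs outside VA are found by telephone. Both stand as limits that the fix must accommodate.

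**Conclusion.** The concern holds as a reconciliation and reporting point. The survey-only ground contradicts the trial's own hypotheses, and no clinical outcome after repair is planned although the committee is referred to harms in the datasets. On full conversion among 102 repaired per arm, Table 3 implies about 12 to 22 more open repairs with the aid. At the largest effect this means about 0.2 to 0.7 more perioperative deaths, with endovascular mortality taken as 2%. These are conditional illustrations rather than predictions in the plan, and they do not show that the aid does net harm. The case for collecting the data rests on being able to report what happened in each arm, since no formal comparison would be informative. The claim about distinguishing facilities by outcome has no planned data behind it.

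**What to change.** - Replace the sentence declining routine harms data, and reconcile the Data and Safety Monitoring Plan with the risks in the Introduction and the hypotheses in the Aim 1 and Aim 2 power analyses.
- At the existing three-monthly CPRS audit, record vital status, death before repair, death within 30 days of repair, aneurysm rupture, re-intervention or unplanned return to surgery, and length of stay. Store timings as time-to-event values, to fit the removal of dates described under Sources of Materials.
- Give the monitoring board counts by arm each quarter for all enrolled Veterans, not only those repaired. Report them descriptively beside the Aim 1 and Aim 2 results, and state that events after repair outside VA may be incomplete.
- Delete the claim about distinguishing facilities by outcome, which the planned data do not support.

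The cost is a protocol amendment and a few minutes per audit, with no new visit, procedure or staff. The counts will be too small to test and should not be presented as evidence of safety.
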